#### Data analysis

The primary outcome of this study is the number of clinics collecting data. Our aim is to get 50% of specialist weight management service using the database. We will report the number of specialist weight management service and what percentage of clinics are using the app at year 2 of the project.

The secondary outcomes of this study are the percentage of patients who we capture data on, and the percentage of data captured on key variables. Our aim to capture data on 60% of patients who attend the services and of those who sign up to the study aim to capture key data on 80% of these patients. The percentage of people we capture the data on will be = (the number of people we have data on/the number of people who attend the clinic) X 100. The percentage of key variable will be worked out for each variable and will be = (number of variable entered/ number of variable possible) x 100.

For the exploratory analysis we will use simple stats (mean, median, SD, interquartile ranges and percentage) to describe the demographic and clinical characteristics of the people entered into the database. Multivariable linear regression will be used to look at the change in weight, BMI, EQ5D and Body Q scores over 12 months and to determine if this is influenced by treatment modality and demographic groups. All analysis will be done in STATA.

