#### SfE CORE Study Protocol

6. **Patient-Reported Outcomes:** Quality of life (EQ5D questionnaire) and well-being (BodyQ questionnaire).
7. **Clinical Treatments:** Interventions received during clinic visits.
8. **Clinical Measures:** Weight, height, BMI, blood pressure.
9. **Relevant Laboratory Results:** HbA1c if has diabetes.

The information gathered through this study will serve to enhance productivity in existing services, inform business planning, and support the establishment of new services. It will also provide critical data to ensure equitable access to weight management services nationwide. Furthermore, the database will function as a registry, enabling researchers to apply for access to data that will advance our understanding and treatment of obesity.

**Study Aim:** This study aims to demonstrate proof of concept for our new data collection system involving a network of weight management clinics across England and Wales. Success would be seen in getting 50% of the current specialist weight management services (there are approximately 49 services at the moment[4]) to capture data on 60% of the patients attending their clinics. Focusing on specialist weight management services in the first instance and then rolling out to other primary care services in a second phase.

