## 2 RATIONALE

As mentioned above there is very little data on who attends specialist weight management services and how effective the interventions offered in these clinics are. This study will enable us to say

1. Whether there is equal access to treatment based on sex, age, social class and ethnicity and if not start to work out what we can do to ensure this does happen.
2. The characteristics of the people attending the specialist weight management services. This data will give an insight as to how unwell this population is and how many people are being referred to these services which will help with planning of services.
3. How effective these services are and whether this varies from area to area. If we find specific models that are working well we can highlight these to the other clinics.
4. Some insight into the “real world” effectiveness of different types of interventions. This is particularly important with two new obesity drugs now being offered on the NHS.

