### 3.2 Outcomes

	Objectives	Outcome Measures	Timepoint(s)
Primary	To demonstrate that our system can be integrated into specialist weight management services clinics and collect data on patients attending clinics.	The number of clinics using the system by end of year 2 of the project. Our aim would be to have 50% of specialist weight management services using this system.	24 months
Secondary	To demonstrate that key outcomes are captured in sufficient quantity to give a fair representation of the people attending the clinics	That the clinics on average are collecting data on 60% of the patients that attend their clinics and on these they have at least 80% data on our key outcomes which are  Demographics Age, sex, socioeconomic status, ethnicity, marital status and employment status and Job.	Baseline  Baseline

SfE CORE Study Protocol

		
Weight history Birth weight, age weight problem started at, highest and lowest weight. Current weight.
 
Previous Weight Loss Attempts Previous Bariatric surgery – Y/N – if Y when and Type. Attempts at commercial diets – Y/N if Y when and Type Tried weight loss medication – Y/N if Y when and Type
 
Medical and drug history List of medical problems with date started. List of drugs taking with dose, frequency and start date.
 
Clinical Treatments Diet and Exercise advice Y/N if yes details and date offered Low calorie diet Y/N if yes details and date started and finished. Specific help with eating habits Y/N, If yes details and date (S) delivered Sessions with psychologist Y/N, If yes details and date (s) delivered. Weight loss drugs Y/N if yes which type and when started. Referred for surgery Y/N if yes when.
 
Patient-Reported Outcomes EQ5D and Body Q
 
Clinical Measures Weight, height, BMI, blood pressure.
	
Baseline
 
Baseline and every 12 months until leaves clinic.
 
Baseline and every 12 months until leaves clinic.
 
Baseline and every 12 months until leaves clinic.
 
Baseline and every 12 months until leaves clinic.
 
Baseline and every 12 months until leaves clinic.
 
Baseline and every 12 months until leaves clinic.

--	--	---	---

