#### SfE CORE Study Protocol

engage more in their health care by using the entirety of the app.		
EQ5D and Body Q questionnaire will be available for the patient to complete		Every 3 months patients will be prompted to update their information
Patient support groups pertinent to the care of these patients will be highlighted on a separate tab in the app		

Data from clinic appointments will be entered by healthcare professionals or those with delegated access per site. These people will check the data that the patient has put in and correct if mistakes have been made. In addition, they will enter weight, height and blood pressure readings from the clinic appointments, HbA1c if measured and details on any treatments offered. Finally, they will assess the severity of the patient's medical health using the Kings and Edmonton scores and record this on the *PeopleWith* dashboard. This data entry will be repeated after each clinical visit.

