#### SfE CORE Study Protocol

in scope, falling short of achieving a comprehensive national overview. Should this project succeed in gathering adequate data, this system will be commissioned as the NHS-standard platform for such data collection.

Our target is to engage 50% of specialist weight management service to use this system and capture 80% of essential data points for 60% of patients attending these clinics. Each weight management service typically receives approximately 700 patient referrals annually, with patients spending an average of 18 months in the program. We plan to recruit patients for two years, tracking outcomes for the duration of their clinic attendance. Data entry can be retrospective, allowing us in the first year to gather data on approximately 1,050 existing patients ( $700 \times 1.5$ ) and 700 newly referred patients each in the first and second years, leading to a potential recruitment of 2,450 patients per service.

Assuming an 80% capture rate, we anticipate enrolling 1,960 patients per clinic, resulting in a total of 41,160 patients across 21 participating sites.

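### The 12-month change regression makes no allowance for clinic, so standard errors would be too small for covariates unevenly spread across clinics, and it describes mainly patients still attending

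*Protocol*

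**What the plan says.** Section 4, Data analysis, names the method: "Multivariable linear regression will be used to look at the change in weight, BMI, EQ5D and Body Q scores over 12 months", and gives its purpose: "to determine if this is influenced by treatment modality and demographic groups". Clinic is not among the influences named, and no clinic effect, random effect or clustered variance is mentioned. The analysis is exploratory; the same paragraph opens with "For the exploratory analysis we will use simple stats".

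The design is multicentre. Section 6.2.1 anticipates enrolment "resulting in a total of 41,160 patients across 21 participating sites". The study aim in section 1 puts the number of services higher ("there are approximately 49 services at the moment"), so the 50% target would mean 24 or 25 sites. Item 3 of the Rationale lists among the questions to be answered: "How effective these services are and whether this varies from area to area".

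On timing, the outcome table in section 3.2 schedules the follow-up measures as "Baseline and every 12 months until leaves clinic", and section 7.5 ends data collection six months after the 24-month recruitment period. Clinic staff enter weight far more often than yearly: "This data entry will be repeated after each clinical visit" (section 4, Data collection).

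**The concern.** Patients in one clinic share staff, local population and treatment offer, so their outcomes are likely to be correlated. A linear regression without clinic treats them as independent. For a covariate whose frequency differs between clinics, this does two things. The reported standard error is too small. In addition, a clinic that does well for other reasons lends part of its result to whichever treatment or group is common there. Treatment modality is an obvious candidate. Socioeconomic status is another, because it is derived from postcode, and ethnicity plausibly follows geography too.

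The regression as described also cannot answer the Rationale's question about variation between areas, because nothing in it represents clinic or area.

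Separately, a single 12-month change needs a 12-month value. Scheduled collection stops when the patient leaves the clinic or data collection closes, so the result mainly describes patients who stayed.

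These are the study's only results on effectiveness and equity of outcome, and the protocol intends the data for service planning.

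**Working it through.** **1. The plan's own size (section 6.2.1).** 700 × 1.5 = 1,050 existing patients, plus 700 + 700 new ones, gives 2,450 per service. 2,450 × 0.80 = 1,960, and 1,960 × 21 = 41,160, as stated. With the 60% patient target instead, 2,450 × 0.60 = 1,470 per clinic. The number of sites is 21 (half of the 42 clinics in the Background) or 25 (half of 49 is 24.5, rounded up).

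**2. Evaluable patients per clinic.** Data collection ends at month 24 + 6 = 30, so anyone enrolled after month 18 cannot reach 12 months. Assume uniform entry of new patients, existing patients enrolled at the start, and a mean stay of 18 months.

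- Fixed 18-month stay: new 1,400 × 18/24 = 1,050; existing with at least 12 months left 1,050 × 6/18 = 350. The total is 1,400, or 57% of 2,450. At 60% to 80% capture this is 840 to 1,120.
- Exponential stay: exp(−12/18) = 0.513; new 1,050 × 0.513 = 539; existing 1,050 × 0.513 = 539. The total is 1,078, or 44%. At 60% to 80% capture this is about 650 to 860.

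**3. Variance inflation when clinic is ignored.** For a coefficient from ordinary regression, inflation = 1 + (m − 1) × ICC of outcome × ICC of covariate. Its square root is the ratio of true to reported standard error. The type I error of a nominal 5% test is 2(1 − Φ(1.96/ratio)). The protocol gives neither ICC, so both are assumed. With m = 800:

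| Covariate ICC | Outcome ICC | Inflation | SE ratio | Type I error |
|---|---|---|---|---|
| 0 (evenly spread) | 0.01 or 0.05 | 1.00 | 1.00 | 5% |
| 0.1 | 0.01 | 1.80 | 1.34 | 14% |
| 0.1 | 0.05 | 5.00 | 2.23 | 38% |
| 0.3 | 0.01 | 3.40 | 1.84 | 29% |
| 0.3 | 0.05 | 12.99 | 3.60 | 59% |

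Across the four uneven rows, the SE ratio runs from 1.28 to 3.28 with m = 650, 1.36 to 3.69 with m = 840, and 1.46 to 4.22 with m = 1,120.

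**4. Simulation check.** With 21 clinics of 500 or 1,000 patients, no true effect and 600 runs per setting, ordinary regression rejected 10% to 41% of the time at covariate ICC 0.1 and 20% to 59% at 0.3. With an evenly spread covariate it rejected 4% to 7%. Adding clinic effects brought rejection to about 3% to 6% in every setting.

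**5. Who lacks a 12-month value.** Study end alone removes new patients enrolled in months 18 to 24: 1,400 × 6/24 = 350 per service, or 14% of 2,450. Clinic exit before month 12 removes none of the new patients under a fixed stay and 1 − 0.513 = 49% under an exponential stay. The protocol does not give the distribution of stay, so the loss through exit is not known.

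**The case against.** The strongest reply is that the protocol is silent on clinic and does not exclude it. Linear regression with clinic indicators or clustered errors would fit the text, and a statistical analysis plan, not seen here, may supply them. The analysis is exploratory, no significance level is set, and the primary and secondary outcomes (clinics using the system, data captured) do not depend on it. This lowers the priority. It does not remove the point, because the protocol chose to name a method and its influences, and clinic is missing from a multicentre analysis whose Rationale asks about differences between areas.

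A reader might infer that every standard error is far too small and that nearly any difference would look significant. The documents do not support that. They give no ICC, and a covariate spread evenly across clinics, as sex might be, is hardly affected. A reader might also take the inflation for an exposure fixed by clinic, 1 + 839 × 0.01 = 9.4 to 1 + 839 × 0.05 = 43 at m = 840. Treatment modality and demographic group are recorded per patient, so that is an extreme case and not the expected one.

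A third tempting reading is that only patients still attending contribute. App prompts every three months and retrospective entry could supply some other values, and some losses come from study end and not from clinic exit. Nor can the 49% early-exit figure be paired with 840 patients per clinic: the first needs an exponential stay, the second a fixed one.

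**Conclusion.** The point holds in a limited form. As written, the regression makes no allowance for clinic. For covariates unevenly spread across clinics its standard errors would be too small, and clinic differences would be partly credited to treatment. Under the assumed ICCs (outcome 0.01 to 0.05, covariate 0.1 to 0.3) and 800 evaluable patients per clinic, the true standard error is about 1.3 to 3.6 times the reported one, falling to no understatement when the covariate is balanced. The size rests on those assumed ICCs and on the assumed pattern of stay; the direction does not. The 12-month change describes mainly, not only, patients still attending, and the documents do not allow the resulting bias to be sized. Because the analysis is exploratory and the primary outcome is untouched, this is a change that should be made, not an obstacle to the study.

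**What to change.** In section 4, Data analysis:

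- Add clinic to the regression as a fixed or random effect, with the baseline value of the outcome as a covariate.
- Use cluster-robust standard errors with a small-sample correction suited to about 21 to 25 clinics.
- Report the between-clinic variation, which addresses item 3 of the Rationale.
- As a supporting analysis, use the weights already entered after each visit in a longitudinal model with random intercepts and slopes for both patient and clinic. Intercepts alone would not cover variation in change between patients or clinics. Note as a limitation that visit timing may itself depend on progress.
- Report how many patients have no 12-month value, split by reason: left the clinic, or study end.

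No new data are needed. The cost is wider confidence intervals for the affected covariates and a little more analysis work. With clinic fitted as a fixed effect, treatment and demographic coefficients become within-clinic contrasts, and the report should say so.

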#### SfE CORE Study Protocol

2. For the centres entering data to capture data on 60% of the patients attending their clinics.
3. To compare the data entered by 100 patients to that collected by a doctor in their initial interview. This will validate that data entry by patients is reliable.
4. To demonstrate that key outcomes are captured in sufficient quantity to give a fair representation of the people attending the clinics.
5. To describe the demographics and clinical characteristics of people attending the specialist weight management services who sign up to the study.
6. To look at changes in weight and well-being over the time in clinic and whether this is affected by treatment modality.
7. To explore potential disparities in access to specialist weight management services based on demographic factors (e.g., ethnicity, socioeconomic status).
8. To explore potential disparities in outcomes from specialist weight management services based on demographic factors (e.g., ethnicity, socioeconomic status).
9. To explore this methodology in collecting data on these characteristics from those patients who attend weight management services in primary care settings.

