**SfE CORE Study Protocol**

		Relevant Laboratory Results: HbA1c if has diabetes.	months until leaves clinic.
Exploratory	
Demographic and clinical characteristics of people attending clinics.
 
To look at changes in weight and well-being over a year and whether this is affected by treatment modality
 
To explore potential disparities in access to specialist weight management service based on demographic factors (e.g., ethnicity, socioeconomic status).
 
To explore potential disparities in outcomes from specialist weight management service based on demographic factors (e.g., ethnicity, socioeconomic status).
 
To explore the outcomes and data collection within primary care additional to specialist weight management services.
	
All key measures mentioned above
 
Changes in Weight and Wellbeing - Weight, BMI, EQ5D and Body Q scores changes over 12 months. Comparison of these changes between different treatment modalities.
 
Access Disparities: Assess whether certain demographic groups are underrepresented in specialist weight management services
 
Outcome Disparities: Analyse differences in clinical outcomes across various demographic subgroups
 
Expectation: building for the future with expectations of services potentially moving from secondary/tertiary care to primary care sites especially in the role of GLP1 treatments
	
Baseline
 
Baseline and every 12 months.
 
Baseline and every 12 months.
 
Baseline and every 12 months.

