#### **6.2.1 Size of sample**

We have not conducted a formal power calculation for this study. The primary objective is to evaluate whether this database can collect sufficient data from specialist weight management service to develop a national profile of patients attending these clinics, the treatments provided, and the effectiveness of these treatments. Previous efforts to collect data from these clinics have been limited

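### If treatment modality and demographic group enter the same regression, the outcome-disparity estimate leaves out disparity that arises through unequal treatment

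*Protocol*

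**What the plan says.** The Data analysis part of section 4 gives the modelling in one sentence. Its method and outcomes are: "Multivariable linear regression will be used to look at the change in weight, BMI, EQ5D and Body Q scores over 12 months". The second half of that sentence gives the purpose of the regression, which is "to determine if this is influenced by treatment modality and demographic groups". It lists no covariates and does not say how many models will be fitted.

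Elsewhere the protocol keeps the two questions apart:

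- **Section 3.1, objective 6:** "To look at changes in weight and well-being over the time in clinic and whether this is affected by treatment modality".
- **Section 3.1, objective 8:** "To explore potential disparities in outcomes from specialist weight management services based on demographic factors".
- **Section 3.2, exploratory outcomes:** the treatment measure is "Comparison of these changes between different treatment modalities". The disparity measure is "Analyse differences in clinical outcomes across various demographic subgroups", with no mention of holding treatment fixed.

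The first item of the Rationale (section 2) is "Whether there is equal access to treatment based on sex, age, social class and ethnicity". The protocol therefore treats unequal treatment between groups as an open question.

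**The concern.** Objectives 6 and 8 need different adjustment. For objective 6, demographic characteristics may influence both the treatment received and the outcome, so they belong in the model as confounders. For objective 8, the treatment received may be one of the routes by which group membership leads to a different outcome. Conditioning on it closes that route.

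A single mutually adjusted model suits objective 6. For objective 8 it answers a narrower question: how outcomes differ between groups whose members had the same treatment. A group that loses less weight because it is less often given an effective treatment could then show a small or null coefficient.

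No other stated measure picks this up. The access measure in section 3.2 concerns whether groups are under-represented in the services, not which treatment they receive once there.

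**Working it through.** **Inputs from the protocol.** The method, the two sets of factors and the four outcomes (weight, BMI, EQ5D, Body Q) come from section 4. The two objectives and their measures come from sections 3.1 and 3.2. The protocol gives no modality effect, uptake by group or standard deviation, and section 6.2.1 says "We have not conducted a formal power calculation for this study". Its only size figure is the expected enrolment, which reproduces: (700 × 1.5 + 700 + 700) × 0.80 × 21 = 2,450 × 0.80 × 21 = 41,160. The point does not depend on it.

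**Formula.** Take two groups, A and B, and one modality.

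- E = extra weight loss from the modality, assumed equal in both groups
- pA and pB = the proportions receiving it
- D = the direct difference in weight loss between the groups at equal treatment

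Group difference without modality in the model = D + E × (pA − pB).

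Group difference with modality in the model = D.

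Part removed = E × (pA − pB).

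**Range (assumed inputs).**

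- E = 5 kg, gap 10 points: 5 × 0.10 = 0.5 kg
- E = 10 kg, gap 20 points: 10 × 0.20 = 2.0 kg
- E = 15 kg, gap 30 points: 15 × 0.30 = 4.5 kg

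**Check by least squares.** This used 400,000 simulated patients per case, with an assumed E of 8 kg and SD of 8 kg. Values are the group coefficient in kg; the value in brackets is from the formula without modality.

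| Uptake A vs B | Direct difference D | Without modality | With modality |
|---|---|---|---|
| 50% vs 30% | 0 | 1.60 (1.6) | 0.01 |
| 60% vs 20% | 0 | 3.23 (3.2) | 0.04 |
| 50% vs 30% | 1 | 2.63 (2.6) | 1.02 |
| 50% vs 50% | 1 | 1.03 (1.0) | 1.03 |

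Modality in the model removes the part that runs through unequal uptake and nothing else. The direct difference stays. With equal uptake the two models agree.

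**The case against.** The strongest reply is that section 4 names a method, not a model. Four outcomes already imply at least four regressions. No covariates are listed, and a demographic model plus a separate modality model would also count as multivariable regression. Sections 3.1 and 3.2 keep the questions apart, and the disparity measure there is worded without conditioning on treatment. The number of models and the covariates in each are ordinary content for a statistical analysis plan, which is not at hand. The analyses are exploratory, and treatments are recorded per patient, so uptake by group could be tabulated.

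Most of this stands. A reader might infer that the plan commits to one joint model and will therefore adjust disparities away. The text does not say so, and separate models are compatible with it. A missing covariate list is not the point either.

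What remains is that the one modelling sentence joins the two sets of factors, and its most natural reading enters both together. On that reading the result does not match the section 3.2 disparity measure. A tabulation of uptake would help, but the protocol does not name one, and it would not give the disparity in outcome.

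**Conclusion.** The point holds in conditional form. If modality and demographic group are entered together, the group coefficient estimates disparity at equal treatment and omits the part due to groups receiving different treatments. That is a legitimate quantity, but not the one section 3.2 describes.

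The size for this study is unknown. The 0.5 to 4.5 kg range rests wholly on assumed effects and uptake gaps, and on a modality effect that is the same in each group.

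Two stronger conclusions are tempting and not supported:

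- **That the adjusted disparity would be zero.** This happens only if there is no direct difference between groups.
- **That the equity aim is defeated.** This would need a joint model to be the only one reported and uptake to be in fact unequal. The documents establish neither.

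No primary or secondary outcome is affected: those concern clinic uptake, patient capture and data completeness. This is a worthwhile improvement to an exploratory analysis.

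**What to change.** In the Data analysis part of section 4, separate the two questions.

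1. **Objective 8, main estimate:** regress each 12-month change on demographic group without treatment modality, adjusted for the baseline value and for other demographics as appropriate.
2. **Objective 8, second estimate:** add modality and report the result as the disparity at equal treatment, beside the first.
3. **Service:** show the objective 8 estimates with and without adjustment for service. The Rationale asks whether effectiveness varies by area, so service may also lie on the path from group to outcome.
4. **Objective 6:** keep demographics in the model as confounders of modality.

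The variables are already in the planned data collection. The cost is a few sentences in the protocol and one extra set of models to run and report.
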